5.7 Enrollment / Consent Plan and Materials

Enrollment will occur in the online platform United in Research.

- <https://www.unitedinresearch.com/volunteers-for-covid-19-experimental-treatment-studies>

Enrollment plan:

- If registered through United in Research as a Citizen Scientist – in an area where Bamlanivimab (LY3819253) at-home infusion is currently available – enrollment experience is agreeing to: daily tracking for symptoms via ProtectWell, to being tested for COVID-19 upon reporting symptoms, to receiving the one-time at-home infusion of Bamlanivimab (LY3819253) if positive for COVID-19 and to provide wellness checks from Day 1-28 after receipt of Bamlanivimab (LY3819253).

Note: No participants will be able to begin tracking for symptoms via ProtectWell if they have not reviewed and signed the complete consent experience through receipt of Bamlanivimab (LY3819253) and ongoing wellness checks post-infusion. This will keep participants informed about what the overall experience will entail should they contract COVID-19 and avoid making any less informed decisions during the period of reporting symptoms and awaiting COVID-19 results. Participants are free to withdraw at any time and will be reminded of this throughout their experience. This balances the request for consent up-front for a product they may never require if they do not contact COVID-19.

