1. QUALITY CONTROL, MONITORING AND REPORTING

9.1 Issues Management Plan

There are two potential sources of issues that may be experienced during participation in the study. We will limit monitoring and reporting to those participants who receive Bamlanivimab (LY3819253).

Participant Reported Issues:

Participants will track daily how they are feeling from Day 1 post-infusion (their baseline of how they are currently feeling) through Day 28 (end of active study). This tracking will be conducted via the ProtectWell application and will have two potential outcomes: 1) Participant indicates they are feeling the same or better (no further follow-up needed) or 2) Participant marks they are feeling worse and there will be a reminder notification via ProtectWell if they are experiencing severe/life-threatening symptoms to seek help and it will trigger a clinical follow-up with that participant (clinical follow-up will occur via phone outreach to result in a discussion with the participant). Based on the discussion, one of the following may occur: 1) participant is OK to remain at-home and on study or 2) participant should seek medical care and are marked as meeting an end point (and we will track outcome of what they needed and if they required hospitalization).

In addition, when speaking to the participant, the clinical team will attempt to ascertain if the issue is: 1) related to worsening COVID-19 symptoms, 2) a potential side effect of Bamlanivimab (LY3819253) or 3) any other unanticipated event that might occur during active study participation. If the issue is potentially related to a side effect of Bamlanivimab (LY3819253), the clinical team will engage the UHG R&D clinical support team (internal R&D team with nurse management oversight for connection for clinical consult when needed) and that project support team will report the issue to Eli Lilly and Company if determined by the PI or delegate to be an unexpected and likely related to the study event (related to receiving Bamlanivimab (LY3819253) – not related to COVID-19 infection which is not due to participating in the study).

Optum Infusion Reported Issues:

Optum Infusion has three potential touch points with the participants in the study:

Pre-Infusion:

- Any issues that arise during the contact call to set up shipping the drug and scheduling the at-home infusion visit
- Any issues that arise during the period from scheduling the at-home visit through to infusion visit

Infusion Visit:

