4.2 Data Collection

The data sources for study participants and the pool of potential controls are not all the same because we don't enroll matched controls in this study. To make sure both groups are symptomatic, we will use Optum electronic medical record (EMR) data to select symptomatic COVID-19 cases as candidates of control, while this information for study participants comes from ProtectWell symptoms data. We summarize the data sources for study participants and matched controls in Table 1.

For enrolled participants, tracked data collection begins from first report of symptoms via ProtectWell. The data collection timepoints are:

1. First report of symptoms
2. COVID-19 test result (positive – moves forward; negative – resets the experience)
3. Date of receipt of Bamlanivimab (LY3819253) via infusion (Day 1)
4. Day 1 infusion (pre, during, post) collection of CRF data (participant vitals/health information and any events experienced)
5. Day 1 post-infusion baseline wellness check through Day 28 final wellness check
6. Any point during Day 1 post-infusion baseline through Day 28 where wellness check indicates participant is feeling worse
7. Point from participant marking feeling worse through action taken (live daily check-in via clinical support, recommendation to seek medical care and/or requiring hospitalization)

Regarding the timeline, the overall duration for enrolled participants is up to 6 months with symptom tracking only. Once an enrolled participant becomes a study participant after reporting symptoms, it is up to 38 days (28 days of active participation after receipt of infusion on Day 1 and up to 10 days from report of symptoms to receive infusion). For matched controls, the active insurance coverage after date of symptoms onset should be up to 38 days. We require matched controls to remain enrolled in utilized data sources to assure data availability. Similar to enrolled participants, matched controls may die after the synthetic date of treatment.

Commented [WWY1]: Would suggest to add A figure to illustrate study design, including screening and treatment time point and assessment period

Commented [JAT2R1]: Thanks for the suggestion. I added a sentence directing the audience to Figures 2 and 3 on the screening process and timeline.

Table 1. Main data sources of study participants and the potential pool of controls.

Study population	Data name	Data description

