4.4 Study Population

4.4.1 Selection Criteria

Both study participants and matched controls will meet the inclusion and exclusion criteria below.

Inclusion Criteria:

- Age 65+, confirmed SARS-CoV-2 positive, located in an area where Bamlanivimab (LY3819253) is available for infusion
- Have mild or moderate COVID-19 symptoms (after stage 1 of symptom tracking)

Commented [JAT4]: Update to keep the same criteria in the latest protocol (version 10 on Feb 3, 2021).

Commented [JAT5]: Remove it as it is no necessary for active participants and controls.

- Control only: Confirmed symptomatic COVID-19 through Optum EMR data.

Exclusion Criteria:

- Current (from first symptom report) hospitalization for COVID-19
- Prior administration of Bamlanivimab

Commented [JAT6]: Remove as not necessary per the EUA.

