4.4.2 Patient Groups

Before analysis there are two study populations – study participants and the pool of potential controls. For study participants, we plan to enroll aged 65 and older, who are deemed high risk per the emergency use authorization, if contracting COVID-19. For the pool of potential controls, we plan to utilize UHC members who have Optum EMR data to confirm presence of symptoms during COVID test as well as having continuous enrollment to access to their claims and prospective hospitalization and death data. If applicable, non-UHC members or UHC members who did not seek care at OptumCare facilities may be used as members of the control population based on EMR review and matching to enrolled participants.

During analysis (i.e., after matching), there will be two study populations – study participants after matching and matched controls. Note that the size of study participants after matching may be smaller than the size of original study participants if a matched control can't be identified.

The targeted number of enrolled participants for tracking for symptoms is 500,000, and the targeted number of study participants who are COVID-19 positive and consent to receive Bamlanivimab (LY3819253) is 7,500. Figure 2 illustrates the process to identify study participants. Regarding controls, we set the case:control ratio at 1:1 and plan to identify 7,500 matched controls which is the same as number targeted for study participants.

Given the current enrollment speed (as of March 9, 2021) and the decreasing COVID-19 hospitalization rate across the US, we may not achieve the target number of study participants, 7,500. However, according to the power analysis in Section 4.3, it is sufficient to have 1,000 study participants with another 1,000 matched controls to detect a 33% decrease in the hospitalization rate (i.e., from 15% to 10%) with power 0.8 and level 0.05.

Commented [JAT7]: Remove as treatment is allowed in this situation per the EUA.

Commented [JAT8]: Remove prior vaccination from exclusion criteria as this is not required per the EUA.

Commented [WWY9]: Should we replace continuous member enrollment?

Commented [WWY10]: Given current enrollment speed, it will be helpful to show what is the minimal sample size for Bam treated group required for the primary objective analysis.

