5.1.1 Populations for Analyses

We define the analysis populations in Table 3 along with the analysis we will conduct. All patients meet the study eligibility criteria. Note that all populations for analyses are UHC members, and the following proposed analytical methods are for UHC members. We may see non-UHC members satisfying the study eligibility criteria, but we cannot obtain or have very limited information of their comorbidities, demographic (e.g., area of residence, socioeconomic index), and if having immunosuppressive treatment prior to COVID-19 diagnosis.

Table 3. Population for analyses

Population	Data for analysis	Definition/Data
Study participants	Disposition analysis and safety	Study participants who sign informed consent and receive Bamlanivimab in single infusion of 700 mg.
Pool of potential controls	Formation of the control group Pre-matching identification of risk factors Estimation of prognostic scores	Patients who meet the study eligibility criteria but did not receive Bamlanivimab.

Commented [WWY23]: Would suggest to revise to include general results reporting, definition of the analysis populations, analysis methods, definition of baseline Refer to attached sample SAP

Overall population	Descriptive analyses Propensity score matching	Consists of study participants and pool of potential controls.
Propensity score matched population	Efficacy and descriptive analyses	Subset of the overall population consisting of study participants and matched controls after propensity matching.
Double score (propensity score and prognostic score) matched population	Sensitivity analyses	Subset of the overall population consisting of study participants and matched controls after double matching.

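### SAP Table 3 does not say whether consented, COVID-positive enrollees who were never infused may serve as controls, and the SAP gives them no analysis population or disposition

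*SAP*

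**What the plan says.** SAP 5.1.1, Table 3, sets the analysis populations. The treated group is "Study participants who sign informed consent and receive Bamlanivimab in single infusion of 700 mg". The pool of potential controls is "Patients who meet the study eligibility criteria but did not receive Bamlanivimab".

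Elsewhere the same label is attached earlier in the pathway. SAP 4.2 places the change of status at symptom report: "Once an enrolled participant becomes a study participant after reporting symptoms". SAP 4.4.2 places it at a positive test plus consent: "the targeted number of study participants who are COVID-19 positive and consent to receive Bamlanivimab (LY3819253) is 7,500". Consent comes before any tracking (Protocol 5.7, Enrollment / Consent Plan): "No participants will be able to begin tracking for symptoms via ProtectWell if they have not reviewed and signed the complete consent experience". Every positive enrollee has therefore already consented. Up to 10 days may pass between symptom report and infusion (SAP 4.2), and withdrawal is allowed at any time (Protocol 5.7).

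On eligibility, SAP 4.4.1 states "Both study participants and matched controls will meet the inclusion and exclusion criteria below". One exclusion is "Current (from first symptom report) hospitalization for COVID-19". Controls must also have symptomatic COVID-19 confirmed in Optum EMR.

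SAP 5.4 defines completion and early discontinuation over the 28 days after infusion. Protocol 9.1 limits monitoring and reporting to infused participants.

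**The concern.** Between the positive test and the infusion a person can worsen, be admitted, withdraw or miss the window. Table 3 takes that person out of the treated group, and its control wording does not keep the person out of the control pool. If the reasons for not being infused are linked to worsening illness, higher-risk people leave one side of the comparison and some may appear on the other. Both effects would favour the drug.

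The loss would also be hard to see. No population in Table 3 is meant for these people, and the written disposition analysis starts after they have gone. With external controls and no randomization, readers need to know how many positive enrollees did not reach infusion and what happened to them.

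**Working it through.** **1. Can a non-infused enrollee be a control under the text?**

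| Requirement | Source | Non-infused positive enrollee |
|---|---|---|
| Did not receive the drug | SAP Table 3 | Meets it |
| Age, positive test, area, mild or moderate symptoms | SAP 4.4.1 | Meets it |
| UHC member | SAP 5.1.1 | Some do |
| Symptoms confirmed in Optum EMR; drawn from EMR plus claims | SAP 4.4.1, 5.8.1.2 | Only those with such a record; enrollees report in ProtectWell and mostly test at home |
| Not hospitalized for COVID-19 | SAP 4.4.1 | Met if never admitted; depends on the check date if admitted |
| Not enrolled in the study | No selection rule | SAP 4.2 says controls are not enrolled, but only to explain why the data sources differ |

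Entry is possible but not automatic.

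**2. Enrollees admitted before infusion.** If the exclusion runs from first symptom report to the index date, they are barred. If it is checked once, at first symptom report, they are not. The SAP does not choose between these readings for controls. SAP 5.8.1.1 treats admission within 38 days of a positive test as an outcome, and Table 3 assigns that risk-factor step to the control pool. SAP 4.5 does not say what happens to a control admitted before the synthetic date.

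**3. Would such an admission count as a control event?** Control follow-up is 28 days from a synthetic date drawn from participants' delays (SAP 4.5). Assume a uniform draw over days 1 to 10. An admission on day 3 falls after the synthetic date for draws of 1 or 2, which is 2/10 = 20%. An admission on day 8 does so for draws of 1 to 7, which is 7/10 = 70%.

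**4. Scale.** SAP 4.4.2 treats 1,000 per group as sufficient for 15% versus 10% at power 0.8. This is right: the requirement is n = [1.960·√(2·0.125·0.875) + 0.842·√(0.15·0.85 + 0.10·0.90)]² / 0.05² = 686 per group (726 with continuity correction). With 1,000 per group the power is 0.92 (0.91 corrected). The planned difference of 5 points is the yardstick below.

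**5. Illustration with no drug effect.** The background rate p = 15% comes from SAP 4.4.2. The share not infused (w) and their hospitalization probability (h) are assumptions; the documents give neither.

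- Treated rate after removal: t = (p − w·h)/(1 − w)
- Share of matched controls if all are matched: s = w/(1 − w)
- Control rate: c = p(1 − s) + s·h
- Spurious risk ratio: t/p for removal only, t/c if all are also matched as controls with every event counted

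For w = 5%, h = 30%: t = (0.15 − 0.015)/0.95 = 14.21%; s = 0.0526; c = 0.1421 + 0.0158 = 15.79%. The ratios are 14.21/15 = 0.95 and 14.21/15.79 = 0.90. In points, the false difference is 0.79 or 1.58.

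| w | h | Removal only | Removal plus all matched |
|---|---|---|---|
| any | 15% | 1.00 | 1.00 |
| 2% | 30% | 0.98 | 0.96 |
| 2% | 100% | 0.88 | 0.79 |
| 5% | 30% | 0.95 | 0.90 |
| 5% | 50% | 0.88 | 0.78 |
| 10% | 30% | 0.89 | 0.80 |

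The middle column assumes nothing comparable is removed from the controls. The last column is an extreme: steps 1 and 3 show that not all would enter and not all events would count.

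**The case against.** The case against is substantial. The eligibility criteria bind controls too, and the natural reading of the hospitalization exclusion bars anyone admitted between symptom report and index date. If controls admitted before the synthetic date are also dropped, losing pre-infusion admissions from the treated side is symmetric. EMR confirmation, UHC membership and the matching step narrow entry further. Table 3 governs the populations, and Protocol 5.2 defines the 7,500 target by receipt of the drug, so the other uses of the label may be loose prose. Pre-infusion losses are not wholly ignored: Protocol 9.1 lists pre-infusion contacts, Protocol 4.4 lists drop-out date and reason, SAP 5.4 promises a listing of patients who enter and discontinue, and the flow charts (SAP Figures 2 and A1) are not visible to us and may count these losses.

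Much of this stands. A reader might infer that Table 3 transfers pre-infusion failures from the treated arm to the control arm. The documents do not support that. Admitted enrollees enter the pool only under one reading of the exclusion, an admission before the synthetic date is outside the control endpoint window, and a withdrawal is not an outcome event. A reader might also infer that matching would favour these enrollees. That is not supported either: all analysed people are UHC members, volunteering is not a listed covariate, and use of ZIP code is left open.

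What remains is that no rule bars a consented, non-infused enrollee who passes the filters. The EMR filter may even select unfavourably, since a person who worsens is more likely to seek care and generate a record (an inference). The drop-out fields in the protocol do not reappear in SAP 4.7 Phase II.B, discontinuation in SAP 5.4 is timed from treatment, and no mock table covers positives who were not infused.

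**Conclusion.** The point holds as a gap in population definitions and reporting. Three things are missing: a rule on whether consented, non-infused positives may be controls, a check date for the hospitalization exclusion in controls, and an analysis population with disposition for these people.

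Any bias would favour the drug if their risk exceeds the background rate, and would be zero if it equals that rate. Its size cannot be derived from the documents. The illustrated risk ratios, 0.98 to 0.88 for removal only and 0.96 to 0.78 at the extreme, rest entirely on assumed loss and hospitalization rates. They show that modest losses could matter against a 5-point planned difference, not that they will. The correction is worth making because it costs little and closes a route to selection bias.

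**What to change.** 1. In SAP Table 3, exclude from the control pool anyone who signed the study consent.
2. For the analysis populations only, apply the hospitalization exclusion at the index date in both groups (infusion date and synthetic date), so that earlier admissions are handled alike. This does not touch clinical eligibility for infusion.
3. Use one term for positive enrollees and another for infused participants, and reconcile SAP 4.2, 4.4.2 and Table 3.
4. Start disposition in SAP 5.4 at the positive test. Give the number not infused, the reason, and COVID hospitalization and death within 38 days (10 + 28) of first symptom report.

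Claims, BCRT and CDSM are already listed sources for UHC members, so item 4 needs no new data source for them. A supportive comparison counting all positive enrollees from symptom report is optional, since it answers a different question. The cost is SAP wording, one extra table and a slightly smaller control pool.

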5.8.1 Main analytical approach.....	22
5.8.2 Sensitivity Analyses.....	26
5.8.3 Handling of missing data or dropouts.....	27
5.9 Exploratory Analyses.....	28
5.10 Safety Analyses.....	28
5.10.1.1 Extent of Exposure.....	29
5.10.1.2 Adverse Events	29
5.11 Protocol Violations	30
5.12 Other Analyses.....	30
5.13 Interim Analyses	31
5.14 Changes to Protocol-Planned Analyses	31
6. Supporting Documentation.....	32
6.1 Appendix 1: Definitions and Medical Codes.....	32
6.2 Appendix 2: CRF forms or questionnaires	35
6.3 Appendix 3: Mock TFLs.....	39

CONFIDENTIAL

[Protocol number: UHG (J2X-NS-I002)] SAP [v.3]

7. **References.....50**

Table of Abbreviations

LY3819253

CONFIDENTIAL

[Protocol number: UHG (J2X-NS-I002)] SAP [\[v.3\]](#)

1. Revision History

This is the third version of statistical analysis plan (SAP) for the UNITED protocol. We (UHG) update the second version according to the feedback from Eli Lilly.

LY3819253

2. Background and Rationale

The severe acute respiratory syndrome coronavirus 2 (SARS-CoV-2) has resulted in the pandemic spread of coronavirus disease 2019 (COVID-19), which in critical cases results in progressive pulmonary failure, complications with acute respiratory distress syndrome (ARDS), and in some cases death. There is an urgent need for effective therapeutics to modify disease outcomes. Bamlanivimab (LY3819253) is a neutralizing IgG1 monoclonal antibody (mAb) to the spike protein of SARS-CoV-2. It is designed to block viral attachment and entry into human cells, thus neutralizing the virus, potentially preventing and treating COVID-19.

This is an open-label, pragmatic, single-arm observational study of Bamlanivimab (LY3819253) infusion efficacy and safety using matched, real-world, external controls in participants with mild to moderate COVID-19.

3. Objectives

The purpose of this study is to: Determine whether symptomatic high risk COVID-19 participants will have a reduction in hospitalizations compared to a real-world external control population when provided with a combination of symptom tracking and single dose administration of Bamlanivimab (LY3819253) via an at-home infusion visit.

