4.7 Variables/Measures

The primary outcome of interest is COVID-related hospitalization rate in study participants and matched controls. We list all potential covariates in two phases. Phase I covers historical data and Phase II includes post COVID-19 diagnosis information. Phase I historical data will be

collected for both study participants and matched controls. Phase II post-COVID 19 diagnosis data has two parts: data elements to be collected for both study participants and matched controls (Phase II.A), and data elements to be collected for only study participants (Phase II.B).

Phase I - Historical data: Study participants and matched controls:

1. COVID-19-related information:

Variable	Data source for study participants	Data source for matched controls
Date of COVID-19 diagnosis test	ProtectWell	Optum EMR or CDSM
Type of COVID-19 diagnosis test*		
Symptomatic flag during COVID-19 test	ProtectWell (all study participants are symptomatic)	Optum EMR
Previous COVID diagnosis flag	CDSM	Optum EMR or CDSM
Previous receipt of Bamlanivimab	UHC claims	Optum EMR or UHC Claims

*: Please see Table A1 in Appendix 1 for LOINC codes of the PCR and antigen COVID-19 tests.

Commented [WWY15]: This variable won't be used for analysis.

Commented [JAT16R15]: Not necessarily. We'll use it to approximate date of symptoms onset and identify matched controls who got COVID-19 around the same time. Please see the comment below for more details.

Commented [WWY17]: Would also include COVID-19 symptoms, and a timing variable: duration since symptom onset to index date

Commented [JAT18R17]: We will include these data fields if available. Regarding date of symptoms onset, it's approximated to be 2 days prior to date of COVID-19 diagnosis (1 day for overnight shipping of COVID-19 test kit and the other day for PCR test).

2. Demographic:

Variable	Data source for study participants	Data source for matched controls
Age as of 2021*		
ZIP code of residence (may or may not be used for identifying matched controls)		
Urbanization of residence in a zip code level (urban, suburban, rural)		
Region/State of residence		
Race		
Gender		
Flag determining whether a patient resides in a nursing facility – determining a patient does not live at home		

*: Age = 2021 – birth year.

Commented [WWY19]: As obesity is a high risk factor, suggest to include BMI as a covariate in PS matching

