5.1 General Considerations

Statistical analysis of this study will be the responsibility of the sponsor or its designee. All tables, figures, and listings will be created using the data described in Table 1 and Section 4.7 (unless otherwise noted), including data during study participation. While not reflected in a table, figure, or listing, any data collected after study participation (e.g., in the Lilly Safety System or collected through queries to the investigator) may be discussed in a clinical study report (CSR) or integrated summary document when deemed relevant. Unless otherwise noted, displays will include columns for study participants and controls will be displayed.

Not all displays described in this statistical analysis plan (SAP) will necessarily be included in the CSR. Not all displays will necessarily be created as a “static” display. Some may be incorporated into interactive display tools instead of, or in addition to, a static display. Any display described in this SAP and not provided would be available upon request.

Treatment differences will be evaluated based on a two-sided significance level of 0.05 for all efficacy analyses. Ninety-five percent confidence intervals for the estimated event rate, odds ratio/hazard ratio will be provided. While we describe many methods addressing different uncertainties, we may not need to perform all analyses mentioned in the draft. Additional exploratory analyses of the data will be conducted as deemed appropriate. All statistical analyses will be performed using R 3.6 (or a higher version).

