5.7 Prior Medication and Concomitant Therapy

According to the EUA, we consider immunosuppressive medications 6 months prior to date of COVID-19 diagnosis as a potential risk factor of COVID-19 hospitalization. Additional descriptive summaries on prior medications and concomitant therapies could be provided for study participants and matched controls if available.

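### The control pool is screened for bamlanivimab only, and without a date, so controls already given another anti-SARS-CoV-2 antibody can enter the comparator unflagged

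*SAP*

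**What the plan says.** SAP 4.4.1 opens with "Both study participants and matched controls will meet the inclusion and exclusion criteria below". It then lists two exclusions: current hospitalization for COVID-19 and "Prior administration of Bamlanivimab". Protocol 5.3 has the same two.

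SAP 5.1.1, Table 3, describes the pool of potential controls as "Patients who meet the study eligibility criteria but did not receive Bamlanivimab". No date is attached, so the text does not say whether non-receipt is judged up to the synthetic treatment date, up to Day 28, or at any time.

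The only antibody item among the variables in SAP 4.7 is "Previous receipt of Bamlanivimab", taken from UHC claims for participants and from Optum EMR or UHC claims for controls. Apart from immunosuppressants as a risk factor, other therapy is covered by one sentence in SAP 5.7: "Additional descriptive summaries on prior medications and concomitant therapies could be provided for study participants and matched controls if available".

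The stated purpose in SAP section 3 is to learn whether participants "have a reduction in hospitalizations compared to a real-world external control population". Neither document says whether that population is meant to be free of antibody treatment or to reflect usual care, whatever it contained.

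**The concern.** The plan already accepts that an antibody-treated patient does not belong in the control pool, since it removes bamlanivimab recipients and looks for them in claims or EMR. It gives no reason for stopping at one product. A patient aged 65 or over with symptomatic COVID-19 who received a different antibody a few days after diagnosis satisfies every criterion as written.

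If such patients are present, the comparator is an unknown mixture of no antibody and another antibody. The estimate then answers neither the no-antibody question nor a clearly stated usual-care question. It also departs from the planning assumption in SAP 4.3, a 75% reduction taken from a comparison with placebo.

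The missing date is a second gap. If non-receipt is read as never, controls are selected on what happened to them after their index date.

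**Working it through.** **1. Where another antibody could be caught.**

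- *Exclusions (Protocol 5.3, SAP 4.4.1):* bamlanivimab only.
- *Control definition (SAP Table 3):* bamlanivimab only, undated.
- *Covariates (SAP 4.7, 5.2, 5.8.1.1):* no other COVID therapy is named.
- *Censoring (SAP 4.5):* Day 28, or loss to follow-up in participants; receipt of another therapy is not a censoring event.
- *Sensitivity analyses (SAP 5.8.2):* COVID therapy is not among the unmeasured confounders listed. Double-score matching draws on the same pool. The E-value is optional and would not show how many controls were treated.

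Nothing in this list removes or flags such a control.

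**2. The plan's own figures.** SAP 4.3 uses a two-sided 5% two-proportion test with continuity correction, 1:1. With d = p₁ − p₂ and p̄ the mean of the two rates:

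n′ = [1.96·√(2p̄(1−p̄)) + z·√(p₁(1−p₁) + p₂(1−p₂))]² / d², and n = (n′/4)·[1 + √(1 + 4/(n′d))]².

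For 25% versus 6.25% at 90% power, n′ = 76.7 and n = 87.05 per arm, 174.1 in total; Table 2 states 175. For the reduced target in SAP 4.4.2 (15% versus 10%, power 0.8), 686 per arm are needed, or 726 with the correction. At 1,000 per arm the power is 0.923 (0.913 corrected), so calling 1,000 per arm sufficient is correct.

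**3. Dilution.** Let f be the share of controls given another antibody and RRₒ its risk ratio. Neither is in the documents, so both are assumptions. For recipients otherwise comparable to the other controls:

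control rate = 0.15·[1 − f·(1 − RRₒ)]; observed RR = 0.10 / control rate;

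power = Φ{[d − 1.96·√(2p̄(1−p̄)/n)] / √[(p₁(1−p₁) + p₂(1−p₂))/n]}, with n = 1,000.

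Worked case, f = 20% and RRₒ = 2/3: control rate = 0.15 × (1 − 0.2/3) = 0.14; RR = 0.10/0.14 = 0.714; power = Φ[(0.04 − 1.96 × 0.01453)/0.01451] = 0.786.

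| f (assumed) | Control rate | Observed RR | Power | Power, corrected |
|---|---|---|---|---|
| 0% | 15.0% | 0.667 | 0.923 | 0.913 |
| 5% | 14.75% | 0.678 | 0.898 | 0.885 |
| 10% | 14.5% | 0.690 | 0.867 | 0.852 |
| 20% | 14.0% | 0.714 | 0.786 | 0.766 |
| 30% | 13.5% | 0.741 | 0.681 | 0.656 |

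If the other antibody is half as effective (RRₒ = 0.833), f = 20% gives RR 0.690 and power 0.867. If it has no effect, there is no dilution.

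**4. Direction.** Suppose recipients would have had h times the untreated risk of other matched controls. Then control rate = 0.15·[(1 − f) + f·h·RRₒ]. With RRₒ = 2/3 the bias vanishes when h = 1.5, because 1.5 × 2/3 = 1. At h = 2 and f = 10% the control rate is 15.5% and the observed RR is 0.645, which is further from the null than the true 0.667.

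**5. The larger planning effect.** At 25% with a 75% reduction and an equally effective other antibody, f = 20% gives a control rate of 0.25 × (1 − 0.2 × 0.75) = 21.25% and RR = 0.0625/0.2125 = 0.294 instead of 0.25. Power stays near 1.

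**The case against.** The best defence is that this is a pragmatic study against real-world controls. If the intended comparator is usual care, other antibodies belong to it and nothing is diluted. That is a legitimate design, but the plan does not say it was chosen, and removing bamlanivimab recipients sits awkwardly with it. What stands is that the comparator must be stated before anyone can call this contamination.

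Several stronger readings are tempting and are not supported:

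- *That treated controls do enter.* Neither document mentions the use or efficacy of any other antibody. The text shows only that such patients are not kept out.
- *That controls are especially likely to have had one, because they live where infusion is available.* The criterion concerns bamlanivimab availability and says nothing about access to other products.
- *That the bias must be toward no effect.* Step 4 shows that it can cancel or reverse.
- *That the study becomes underpowered.* For 15% versus 10% the SAP claims power of only 0.80, and an assumed 20% still leaves 0.786. The fall from 0.92 is mostly surplus that the plan did not claim.
- *That other therapy cannot be a covariate.* It is not named, but SAP 5.8.1.1 admits further clinical attributes where available, and SAP 5.2 leaves the final list to be confirmed before the outcome analysis.

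The upper shares also need caution. Infusion falls within 10 days of symptoms, and a margin comment in SAP 4.7 places onset two days before diagnosis. Receipt before the synthetic date is thus confined to a short window, where 20 to 30% may be high.

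**Conclusion.** The gap in the text is established: Table 3 and the antibody variable in SAP 4.7 screen for bamlanivimab only, with no date in Table 3, and no planned analysis would reveal controls treated with another antibody. The size of the consequence is conditional. If the other antibody is as effective as bamlanivimab and its recipients are otherwise comparable, an assumed 5 to 30% of controls moves the risk ratio from 0.67 to between 0.68 and 0.74. Power at 1,000 per arm then falls from 0.92 to between 0.90 and 0.68, crossing 0.80 just short of a 20% share. With selection of higher-risk recipients the sign is uncertain.

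A reader might infer that the sample-size figures are wrong or that a null result should be expected; neither follows. No stated figure is in error because of this point. It should be settled before outcome data are accessed, because the comparison cannot be interpreted without knowing what the controls received.

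**What to change.** 1. In SAP Table 3, define the pool of potential controls as eligible patients with no record of any anti-SARS-CoV-2 monoclonal antibody, bamlanivimab included, on or before the synthetic treatment date, identified from UHC claims or Optum EMR. Do not exclude on receipt after that date.
2. In SAP 4.7, broaden the prior-bamlanivimab variable to any such antibody, with its date, in both groups.
3. Report later receipt by group through Day 28, and add a sensitivity analysis that censors at later receipt in both groups.
4. State in the SAP objectives or Table 3 that the comparator is no antibody treatment at index.

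The change belongs in the analysis-population definition. Leave Protocol 5.3, which governs who may be infused, as it is.

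The cost is a short code list and the loss of some controls from the pool. The screen uses sources the plan already searches for bamlanivimab, and it will miss receipt that neither source records.
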